4.6 Rationale for Public Health Emergency mitigation procedures

During a Public Health emergency as declared by Local or Regional authorities i.e. pandemic, epidemic or natural disaster, mitigation procedures to ensure participant safety and trial integrity are listed in relevant sections. Notification of the Public health emergency should be discussed with Novartis prior to implementation of mitigation procedures, and permitted/approved by Local or Regional Health Authorities and Ethics Committees as appropriate.

5 Study Population

The study population will consist of male and female participants ≥ 18 years, with SjS defined according to the American College of Rheumatology/European League Against Rheumatism (ACR/EULAR) 2016 classification criteria ([Shiboski et al 2017](#)) who have completed the entire treatment period up to Week 48 and the mandatory 12 weeks follow-up period up to Week 60 of the TWINSS core study. The study population has previously been described in detail in the core study protocol (refer to Section 5 of the core study protocol). Enrollment will be determined by the number of participants completing the core study. It is estimated that approximately 160 participants may choose to enter the extension study from the core study.

5.1 Inclusion criteria

Participants eligible for inclusion in this study must meet **all** of the following criteria:

1. Participants must have participated in the TWINSS core study, CCFZ533B2201, and must have completed the entire treatment period up to Week 48 and the follow-up period up to Week 60
2. Signed informed consent must be obtained prior to participation in the extension study (i.e. before commencement of the Week 60 assessments of the core study)
3. In the judgement of the Investigator, participants must be expected to clinically benefit from continued iscalimab therapy

5.2 Exclusion criteria

Participants meeting any of the following criteria are not eligible for inclusion in this study.

1. Sjögren's Syndrome overlap syndromes where another autoimmune rheumatic disease constitutes the principle illness, specifically:

- Moderate-to-severe active systemic lupus erythematosus (SLE) with anti-dsDNA positivity and renal involvement, or other organ involvement that impedes on ability to score ESSDAI domains
 - Active rheumatoid arthritis (RA) that impedes on the ability to score the ESSDAI articular domain
 - Systemic sclerosis
 - Any other concurrent connective tissue disease (e.g., lupus nephritis (LN), large vessel vasculitis (LVV), Sharp syndrome (mixed connective tissue disease) that is active and requires immunosuppressive treatment outside the scope of this trial and would impede on Sjögren's Syndrome organ domain assessments
2. Use of other investigational drugs other than iscalimab during the core study
 3. Active uncontrolled viral, bacterial or other infections requiring systemic treatment at the time of enrollment, or history of recurrent clinically significant infection or of bacterial infections with encapsulated organisms
 4. Pregnant or nursing (lactating) women, where pregnancy is defined as the state of a female after conception and until the termination of gestation, confirmed by a positive human Chorionic Gonadotropin (hCG) laboratory test
 5. Women of child-bearing potential (WOCBP), defined as all women physiologically capable of becoming pregnant, unless they are using highly effective methods of contraception during dosing and for 14 weeks after stopping of investigational drug
Highly effective contraception methods include:
 - Total abstinence (when this is in line with the preferred and usual lifestyle of the patient). Periodic abstinence (e.g., calendar, ovulation, symptothermal, post-ovulation methods) and withdrawal are not acceptable methods of contraception
 - Female sterilization (have had surgical bilateral oophorectomy with or without hysterectomy), total hysterectomy or tubal ligation at least six weeks before taking investigational drug. In case of oophorectomy alone, only when the reproductive status of the woman has been confirmed by follow-up hormone level assessment
 - Male sterilization (at least 6 months prior to screening and confirmed as successful). For female patients in the study, the vasectomized male partner should be the sole partner for that patient. In case the vasectomized male partner is not the sole partner of the female patient, highly effective method of contraception must be applied (double barrier contraception is not sufficient)
 - Use of oral, (estrogen and progesterone), injected or implanted hormonal methods of contraception or placement of an intrauterine device (IUD) or intrauterine system (IUS) or other forms of hormonal contraception that have comparable efficacy (failure rate < 1%), for example hormone vaginal ring or transdermal hormone contraception. In case of use of oral contraception women should have been stable on the same pill for a minimum of 3 months before taking investigational drug

Women are considered post-menopausal and not of child bearing potential if they have had 12 months of natural (spontaneous) amenorrhea with an appropriate clinical profile (e.g., age appropriate, history of vasomotor symptoms) or have had surgical bilateral oophorectomy (with or without hysterectomy), total hysterectomy or tubal ligation at least

six weeks ago. In the case of oophorectomy alone, only when the reproductive status of the woman has been confirmed by follow up hormone level assessment she is considered not of childbearing potential.

In case local regulations deviate from the contraception methods listed above, local regulations apply and will be described in the Informed Consent Form (ICF).

6. Missing ESSDAI (Cohort 1 and Cohort 2) or ESSPRI (Cohort 2) scores in the core study at Weeks 0 and 4 or Weeks 40 and 48.

6 Treatment

6.1 Study treatment

6.1.1 Investigational and control drugs

The following drugs will be used in this study and will be administered in accordance with this protocol and where applicable, current local labeling.

- CFZ533 (iscalimab) 300 mg provided in 2.0 mL PFS for s.c. injection
- Placebo provided in 2.0 mL PFS for s.c. injection required for blinding
- CFZ533 (iscalimab) 300 mg provided in 2.0 mL PFS for s.c. administration (open-label (OL) supplies)

Before enrollment in this extension study, all participants electing to continue will sign an Informed Consent form. At extension study entry, participants/caregiver will be provided with detailed instructions for self-administration of the s.c. injection (Instructions for Use (IFU)) using the PFS formulation. In cases where the participant is not comfortable or confident that he/she can successfully self-administer the full dose of PFS in a home setting, a caregiver can be trained to administer the treatment to the participant.

Each injection will be administered by the participant/caregiver into an appropriate injection site of the body. Site staff will administer the injection to participants who are not able or unwilling to self-administer the PFS injection. For the first four visits at Weeks 60E1, 61, 62 and 64, injections will be performed at site. Starting from Week 66 participants will have the choice of self-administration or injection by caregiver (once trained) at home or continuing with administration at site, based on personal preference and the Investigator's clinical judgment.

The study is blinded until the final database lock of the core study to protect the integrity of the data in the ongoing core study. Once study unblinding occurs after the final database lock of the core study, the participants will continue to receive the same dose of iscalimab (either 600 mg or 300 mg) and for those assigned to the 300 mg regimen, they will no longer receive the placebo PFS.

Note: PFS do not need to be prepared at the site. PFS will be packaged both as open-label and double-blind supplies. When the final database lock for the TWINSS core study is achieved, the extension study will become an OL study and the PFS will be provided in an OL manner with no further requirements for placebo PFS injections.

Novartis Global Clinical Supply (GCS) would provide the following IMPs in the trial. No other medication would be supplied by GCS.

Table 6-1 Investigational and control drug

Investigational/ Control Drug (Name and Strength)	Pharmaceutical Dosage Form	Route of Administration	Supply Type	Sponsor (global or local)
CFZ533 300 mg/2 mL	Solution for injection	Subcutaneous Use	Blinded; PFS	Novartis Pharma AG
Placebo/2 mL	Solution for injection	Subcutaneous Use	Blinded; PFS	Novartis Pharma AG
CFZ533 300 mg/2 mL (OL)	Solution for injection	Subcutaneous Use	Open-label; PFS	Novartis Pharma AG

Instructions for administration of CFZ533 (iscalimab) and matching placebo are described in a separate manual.

6.1.2 Additional study treatments

No other treatment beyond investigational drug is included in this trial.

6.1.3 Treatment arms/group

No re-randomization is planned for the extension study. The treatment re-assignment for the extension study occurs at visit Week 60E1 which is the last visit of the core study (Week 60). Upon completion of the core study, Investigators will use their clinical judgment including responder definitions provided below to decide if it is beneficial for participants to continue with the extension study based upon response to therapy at the end of the treatment period of the core study.

Participants will be re-assigned to one of the following two treatment arms:

- Arm 1 - Iscalimab 600 mg s.c. Q2W
- Arm 2 - Iscalimab 300 mg s.c. Q2W

At Week 60 of the TWINSS core study, all eligible participants from the core study can opt to be enrolled in the extension study via IRT. The Week 60E1 visit will be performed on the same day once the Week 60 visit of the core study is completed by the participant. The Investigator or his/her delegate will contact the IRT after confirming that the participant fulfills all the extension study inclusion/exclusion criteria. An IRT algorithm will be programmed to assign the participant to blinded treatment in the extension study using ESSDAI (Cohort 1 and Cohort 2) and ESSPRI (Cohort 2) assessment scores from predefined time points in the TWINSS core study.

- For participants rolling over from Cohort 1 in the TWINSS core study, the change in ESSDAI score between Week 4 and Week 48 will be used to determine if the participant responded to treatment in the core study. If an ESSDAI score is missing at Week 4 and/or Week 48, then Week 0 or Week 40 scores should be respectively used for the algorithm. A decrease of 3 points or more from Week 4 (or Week 0 if the ESSDAI score is missing at Week 4) will classify the participant as a treatment responder in Cohort 1.

- For participants rolling over from Cohort 2 in the TWINSS core study, a change in both ESSDAI and ESSPRI scores between Week 4 and Week 48 will be used to determine if the participant responded to treatment in the core study. If an ESSDAI or ESSPRI score is missing at Week 4 and/or Week 48, then Week 0 or Week 40 scores should be respectively used for the algorithm. A decrease of 1 point or more in both the ESSDAI and ESSPRI scores from Week 4 (or Week 0 if the ESSDAI or ESSPRI score is missing at Week 4) will classify the participant as a treatment responder in Cohort 2.

Week 4 is being used as a baseline assessment to assess change over time, solely for the purposes of re-assigning patients to 300 mg or 600 mg, in a non-randomized manner, in this extension trial and was selected to minimize any potential placebo effect and regression to the mean observed at study treatment initiation in clinical trials.

Taking the treatment received during Treatment Period 2 of the TWINSS core study, and the responder status as the reference, the IRT algorithm will re-assign a dose level for extension study treatment. The maintenance treatment assigned for the extension study will be the same dose as in the core study or a higher dose level (Figure 6-1).

- Participants receiving iscalimab 600 mg s.c. Q2W or 300 mg s.c. Q2W in the core study and who meet the definition of a response will continue with the same dose in the extension study.
- Participants receiving iscalimab 600 mg s.c. Q2W in the core study and who do not meet the definition of a response will continue in the extension study with the same dose.
- Participants receiving iscalimab 150 mg s.c. Q2W in the core study and who meet the definition of a response will be re-assigned to 300 mg s.c. Q2W in the extension study.
- Participants receiving iscalimab 300 mg s.c. Q2W or 150 mg s.c. Q2W in the core study and who do not meet the definition of a response will be re-assigned to 600 mg s.c. Q2W in the extension study.

Figure 6-1 IRT Algorithm for treatment reassignment

TWINSS Core Study Cohort 1 - Datapoints for algorithm		TWINSS Core Study Cohort 2 - Datapoints for algorithm			
ESSDAI	Week 4 (or 0)	ESSDAI	Week 4 (or 0)	ESSPRI	Week 4 (or 0)
	Week 48 (or 40)		Week 48 (or 40)		Week 48 (or 40)
Definition of «Response»	-3 points or more change from Week 4 (or 0)	Definition of «Response»	-1 point or more change from Week 4 (or 0)	AND	-1 point or more change from Week 4 (or 0)
«Responder» if definition met	+		+		+

TWINSS Core Study		Maintenance dose levels assigned for extension study (NOTE: as reference consider the dose level in Treatment Period 2 of core study)
«Baseline»	Response Week 48 (or 40)	
Week 4 (or 0)	+	300 mg and 600 mg patients continue to extension on the same dose 150 mg → go to 300 mg
Week 4 (or 0)	-	600 mg → continue to extension on the same dose 300 mg → go to 600 mg 150 mg → go to 600 mg

+ = Response (definition met for purpose of IRT algorithm)
- = No response

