6.3.2 Treatment assignment, randomization

No re-randomization will be performed in this study. At Week 60 of the core study, all eligible and consenting participants from the core study will be enrolled via Interactive Response Technology (IRT) and will be re-assigned to one of the treatment arms (refer to [Section 6.1.3](#)). An IRT algorithm will be programmed to assign the participant to blinded treatment in the extension study using ESSDAI (Cohort 1 and Cohort 2) and ESSPRI (Cohort 2) scores from predefined time points in the TWINSS core study. ESSDAI and ESSPRI scores at predefined time points will be transferred to the extension study IRT database by the electronic clinical outcome assessment (eCOA) vendor after the Investigator or his/her delegate has confirmed this transfer in the core study (for details, refer to the IRT user guide). The IRT will assign a number to the participant, which will be used to link the participant to a treatment arm and will specify a unique medication number for the first package of study treatment to be dispensed to the participant.

- For participants rolling over from Cohort 1 in the TWINSS core study, the change in ESSDAI score between Week 4 and Week 48 will be used to determine if the participant responded to treatment in the core study. If an ESSDAI score is missing at Week 4 and/or Week 48, then Week 0 or Week 40 scores should be respectively used for the algorithm. A decrease of 3 points or more from Week 4 (or Week 0 if the ESSDAI score is missing at Week 4) will classify the participant as a treatment responder in Cohort 1.
- For participants rolling over from Cohort 2 in the TWINSS core study, a change in both ESSDAI and ESSPRI scores between Week 4 and Week 48 will be used to determine if the participant responded to treatment in the core study. If an ESSDAI or ESSPRI score is missing at Week 4 and/or Week 48, then Week 0 or Week 40 scores should be

respectively used for the algorithm. A decrease of 1 point or more in both the ESSDAI and ESSPRI scores from Week 4 (or Week 0 if the ESSDAI or ESSPRI score is missing at Week 4) will classify the participant as a treatment responder in Cohort 2.

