6.4 Treatment blinding

This will be a double-blind treatment **until the final database lock of Core study**. Participants, Investigator, site staff, and persons performing the assessments will remain blinded to the identity of the treatment until the final database lock of the core study, using the following methods:

1. Treatment assignment data are kept strictly confidential until the time of unblinding and will not be accessible by anyone else involved in the study with the exception of the bioanalyst
2. The identity of the treatments will be concealed by the use of investigational treatments that are all identical in packaging, schedule of administration and appearance

The re-assignment codes associated with participants from whom PK samples are taken will only be disclosed to the PK bioanalysts who will keep the PK results confidential until primary database lock of the core study (Week 24). Blood samples for PK, immunogenicity and ██████████ assessment will be collected for all participants.

Whenever needed or requested by the clinical team, before the open-label part of the extension study, the bioanalyst will share bioanalytical data in a blinded fashion with the pharmacokineticist.

Up to final database lock of core study, unblinding will only occur in the case of subject emergencies (see [Section 6.6.2](#)).

After final database lock of core study, the treatment arm for individual participant will be unblinded and the study will be conducted open-label.

Unblinding of the CTT will occur at the time of the primary database lock at Week 24 for each cohort of the core study.

Table 6-3 Blinding and unblinding plan

Role	Time or Event				
	Treatment re-assignment list generated	Treatment allocation & dosing	Safety event (single participant unblinded)	Primary database lock at Week 24 of core study	Final database lock of core study
Participants	B	B	B	B	U
Site staff	B	B	UI	B	U
PK sample analyst(s)	B	U	UI	U	U
Global Clinical Supply and Randomization Office	U	U	U	U	U

Role	Time or Event				
	Treatment re-assignment list generated	Treatment allocation & dosing	Safety event (single participant unblinded)	Primary database lock at Week 24 of core study	Final database lock of core study
Unblinded Pharmacovigilance sponsor staff	B	UI	UI	UI	U
Data Monitoring Committee (DMC)	B	U	U	U	U
CTT and other sponsor teams (trial team, project team, management & decision boards, support functions)	B	B	B	U	U

Key:

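### Sites told to apply the printed responder definitions can deduce 600 mg for every non-responder before the core lock, so the site-side blind stated in Section 6.4 and Table 6-3 is only partial

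*Protocol*

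**What the plan says.** Four parts of the protocol bear on this.

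- **Continuation decision (Section 6.1.3).** "Investigators will use their clinical judgment including responder definitions provided below to decide if it is beneficial for participants to continue" in the extension. The definitions follow in the same section. An ESSDAI fall of at least 3 points between Week 4 (or 0) and Week 48 (or 40) "will classify the participant as a treatment responder in Cohort 1". For Cohort 2 the criterion is "A decrease of 1 point or more in both the ESSDAI and ESSPRI scores from Week 4" (or Week 0).
- **Dose map (Section 6.1.3, Figure 6-1).** Participants on 600 mg in the core "who do not meet the definition of a response will continue in the extension study with the same dose". Those on 300 or 150 mg "who do not meet the definition of a response will be re-assigned to 600 mg s.c. Q2W in the extension study". Responders on 600 or 300 mg keep their dose, and responders on 150 mg go to 300 mg.
- **Handling of scores (Section 6.3.2).** The eCOA vendor sends the scores to the extension IRT "after the Investigator or his/her delegate has confirmed this transfer in the core study".
- **Blind (Section 6.4).** "Participants, Investigator, site staff, and persons performing the assessments will remain blinded to the identity of the treatment" until the core final database lock. The means are confidential assignment data and treatments identical in packaging, schedule and appearance. Table 6-3 marks site staff as blinded at allocation and dosing and at the Week 24 lock, and as unblinded at the core final lock.

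**The concern.** The blind relies on hiding the assignment and the syringes. Neither hides a dose that follows from a printed rule and from a classification the investigator is asked to make. For non-responders the two sections cannot both be true at the site.

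Safety at two dose levels is the primary objective. Severity and relationship to treatment are recorded for each adverse event at the site (Section 10.1.1). Events by severity and treatment-related events are summarised by treatment group (Protocol Section 12.4.2, SAP Section 2.4). Under the printed rule, non-responder status always points to 600 mg and responder status never settles on 300 mg. Any effect of knowing the dose through this route would therefore fall on the 600 mg arm. A clinical study report (CSR) that repeated Section 6.4 would describe those judgements as double-blind when, for non-responders, the site could have worked out the dose.

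**Working it through.** The plan gives no figure to reproduce. The check is an enumeration of the assignment rule.

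**Step 1. Branches.** The reference dose is the one received in core Treatment Period 2 (Section 6.1.3). Core placebo arms D and F are switched to iscalimab at Week 24 (Section 16.11), so no placebo branch is left over.

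| Core Period 2 dose | Responder | Non-responder |
|---|---|---|
| 600 mg | 600 mg | 600 mg |
| 300 mg | 300 mg | 600 mg |
| 150 mg | 300 mg | 600 mg |

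**Step 2. Reading forward.** For a non-responder, 600 mg is the only possible extension dose, so P(600 mg given non-responder) = 1. For a responder, 300 and 600 mg both remain possible, so responder status alone does not fix the dose.

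**Step 3. Reading backward.** A non-responder on 600 mg is compatible with a core dose of 600, 300 or 150 mg. The core assignment is not revealed.

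**Step 4. Inputs at the site.** Applying the definitions requires the Week 4 (or 0) and Week 48 (or 40) scores. In Cohort 2, failing the ESSDAI part alone already settles non-response. The investigator or delegate confirms the score transfer. Eligibility must also be confirmed before the IRT is contacted, including exclusion criterion 6 on missing scores. No visible text withholds the scores, the responder status or the rule from the site.

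**Step 5. Number affected.** This is the number of non-responders who enter, and the documents give no responder rate. Assuming 20% to 60% non-responders:

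- planned 160 (Section 12.8): 0.2 × 160 = 32 to 0.6 × 160 = 96;
- enrolled 206 (SAP Section 1.1): 0.2 × 206 ≈ 41 to 0.6 × 206 ≈ 124.

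**Step 6. Share of the 600 mg arm.** Let R be the responder rate, taken as equal across core doses, and f the fraction on 600 mg in core Period 2. The share with a deducible dose is (1 − R) / [(1 − R) + R·f]. Neither R nor f is given. Illustrations:

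| R | f | Calculation | Share |
|---|---|---|---|
| 0.3 | 1/3 | 0.7 / 0.8 | 88% |
| 0.5 | 1/2 | 0.5 / 0.75 | 67% |
| 0.6 | 2/3 | 0.4 / 0.8 | 50% |
| 0.8 | 2/3 | 0.2 / 0.733 | 27% |
| 0.9 | 2/3 | 0.1 / 0.7 | 14% |

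The range is too wide to support any statement about most or little of the arm. The contradiction does not depend on it.

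**The case against.** The strongest reply is that the blind exists to protect data in the ongoing core study (Sections 4.1, 4.3 and 6.1.1), and that purpose is not shown to fail. This stands (Step 3). A reader might infer that the double-blind as a whole collapses, but the documents do not support that. The gap covers non-responders only, lies on the site side, and ends at the core final lock, when the study becomes open-label anyway. Section 6.4 nevertheless states a blind on extension treatment and names investigators and assessors, and that statement is inaccurate for this subset.

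A second reply is that site knowledge is inferred. The vendor transfers the scores, the IRT user guide is not available here, and the efficacy-assessment section is redacted, so masking described there cannot be excluded. This stands as a qualification: the right word is deducible, not known.

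A third reply is that little harm follows. Everyone receives active drug, relatedness is a yes/no judgement on study treatment rather than on dose, the analysis is descriptive, and assignment is openly non-randomised. A reader might infer that related events in the 600 mg arm are inflated. Nothing in the documents shows this.

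It may also be said that non-responders would not be enrolled. Section 3 says that all participants will be considered, and the rule has explicit non-responder branches. Selection towards responders could still lower the number affected.

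Finally, a reader might see a further contradiction in the statement that Week 4 serves as baseline "solely for the purposes of re-assigning patients to 300 mg or 600 mg, in a non-randomized manner", since the continuation decision uses definitions built on that baseline. The sentence can also be read as confining the Week 4 baseline to roll-over rather than efficacy analysis. It is loose wording at most.

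**Conclusion.** The point holds as a partial, temporary contradiction between Section 6.1.3 and Section 6.4 with Table 6-3. A site that applies the definitions as told can deduce 600 mg with certainty for each participant it classifies as a non-responder, from Week 60E1 to the core final lock. This rests on one assumption: that the site can see the scores the definitions need, which the instruction implies.

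The number of participants and the length of the window cannot be derived, because responder rates and the lock date are not given. For Cohort 2 the core doses are not stated either, so for its responders nothing can be said beyond what the printed rule shows. An influence on severity, relatedness or ESSDAI scoring is possible but not demonstrated. What needs correcting is the description of the blind.

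**What to change.** **Main change.** Reconcile Section 6.1.3 with Section 6.4 and Table 6-3. State that, before the core final lock, the site-side blind is partial because 600 mg can be deduced for non-responders under the printed rule. Carry the same caveat into the CSR, and do not describe pre-lock adverse event relatedness or efficacy scoring as double-blind for those participants. If scores or responder status were in fact withheld from sites, say how; that would answer the point.

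**Only for sites or participants not yet re-assigned.** Remove the responder definitions from the continuation judgement and hold the cut-offs and dose map in a restricted IRT specification. SAP Section 1.1 reports 206 participants already enrolled, so this cannot help them.

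**Cost.** The main change is a wording amendment and a reporting caveat, with a less favourable description of the blind. The optional step leaves less assignment detail in the site-facing protocol, and because it alters what the continuation judgement draws on, it is more than an edit. No dose or assignment rule changes.

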4.3 Rationale for choice of control drugs (comparator/placebo) or combination drugs

There is no placebo or active control group in this study given the purpose and main objectives are to extend treatment of participants who completed the core study. The use of two different doses of iscalimab (iscalimab 600 mg and 300 mg) will allow evaluation of both doses in terms of safety, tolerability and sustainability of clinical benefits. Placebo injection will be provided

to maintain blinding until the final database lock of the core study to protect the integrity of the data in the ongoing core study. For more details refer to [Section 6.1.1](#).

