2.1 Data analysis general information

Novartis will perform the analyses for this study. Statistical software SAS version 9.4 or later will be used.

Summary statistics for continuous variables will include N, mean, standard deviation, minimum, lower quartile, median, upper quartile, maximum. Summary statistics for discrete variables will be presented in contingency tables and will include absolute and relative frequencies.

If not otherwise specified, two-sided confidence intervals will be displayed. Unless otherwise stated, the level of significance will be set to 5% (two-sided).

All safety listings will be presented by treatment sequence from extension study.

All efficacy/PRO listing will be presented by core study cohort and extension treatment group

Only descriptive statistics will be provided, no inferential statistics will be conducted.

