Full Analysis Set (FAS): The FAS comprises all participants to whom study treatment for the extension study has been assigned by the re-assignment algorithm. For analysis on FAS, participants will be analyzed according to the treatment group to which they have been assigned. Only data in the extension study will be included in the analysis.

Summaries of extension data in FAS will be based on the core study cohort assignment and reassigned treatment groups.

- Cohort 1 CFZ533 600 mg
- Cohort 1- CFZ533 300 mg
- Cohort 2 CFZ533 600 mg
- Cohort 2 CFZ533 300 mg

Safety Set (SAF): The Safety Set includes all subjects who received at least one dose of study treatment. Subjects will be analyzed according to the actual treatment received. The safety set will be used in the analysis of all safety variables.

The actual treatment received in a period is defined as the treatment dose level (including loading dose) that a subject was most frequently exposed to during the period. The frequency will be calculated using data collected on the Dose Administration Record (DAR). In case a subject is exposed to more than one dose level for the same number of times during a period, the actual treatment is the earliest one administered to the subject in that period.

Summaries of extension data in SAF will be based on the re-assigned treatment groups.

- CFZ533 600 mg
- CFZ533 300 mg

The PK Set (PKS) includes all subjects who received at least one dose of iscalimab treatment and have quantifiable PK measurements of iscalimab. Analysis of plasma PK, will be based on PKS and by the iscalimab treatment dose level a subject is most frequently exposed to, including the loading dose, during the study. Only data in the extension study will be included in the analysis.

Summaries of extension data in PKS will be based on the re-assigned treatment groups.

- CFZ533 600 mg
- CFZ533 300 mg

The IM Set (IMS) includes all subjects who received at least one dose of iscalimab treatment and have quantifiable immunogenicity measurements of iscalimab. Analysis of immunogenicity data will be based on PKS and by the iscalimab treatment dose level a subject is most frequently exposed to, including the loading dose, during the study. Only data in the extension study will be included in the analysis.

Summaries of extension data in IMS will be based on the re-assigned treatment groups.

- CFZ533 600 mg
- CFZ533 300 mg

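### Extension dose is fixed by core response and core dose, but the visible plan shows primary safety only as pooled 600 mg and 300 mg columns, so differences between them should not be read as a dose effect

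*Protocol*

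**What the plan says.** Protocol 6.1.3 and Figure 6-1 assign the extension dose by a fixed rule, "in a non-randomized manner, in this extension trial".

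- Core 600 mg or 300 mg participants "who meet the definition of a response will continue with the same dose in the extension study".
- Core 150 mg participants "who meet the definition of a response will be re-assigned to 300 mg s.c. Q2W in the extension study".
- Core 300 mg or 150 mg participants "who do not meet the definition of a response will be re-assigned to 600 mg s.c. Q2W in the extension study".
- Core 600 mg participants "who do not meet the definition of a response will continue in the extension study with the same dose".

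Protocol 12.4.1 makes all safety data primary endpoints. For the Safety Set the SAP states: "Summaries of extension data in SAF will be based on the re-assigned treatment groups". It then lists two groups, 600 mg and 300 mg. SAP 2.4 summarises adverse events, laboratory data and vital signs by treatment on that set. Full Analysis Set summaries are split by core cohort; Safety Set summaries are not. Protocol 12.4.5 to 12.4.7 mark sensitivity, supplementary and supportive analyses as not applicable. SAP 2.1 adds: "All safety listings will be presented by treatment sequence from extension study". It does not define treatment sequence, and the visible safety tables do not use it.

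**The concern.** Protocol 4.3 says that using two doses "will allow evaluation of both doses in terms of safety, tolerability and sustainability of clinical benefits", and Protocol 1.2 and 4.1 say the safety data may inform Phase III design. Side-by-side 600 mg and 300 mg columns invite a dose reading, yet the columns were formed by selecting on outcome and prior dose.

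The documents give reasons why the groups could differ at the same dose. Response is a change in disease activity, and in Cohort 2 also in symptoms. Protocol 6.2 and 6.2.3 allow corticosteroids for poorly controlled disease, and infection is the first potential risk in Table 4-1. This could raise event rates among non-responders. In the other direction, core 600 mg entrants have already completed Period 2 on that dose, which could make the 600 mg column look better. The pooled column also hides any difference between participants who stayed on 600 mg and those moved up to it.

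**Working it through.** The documents contain no sample-size or power figure to reproduce: the planned 160 in Protocol 12.8 is a roll-over estimate. The check has four steps.

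**1. Enumerate the rule (Protocol 6.1.3; no assumptions).**

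| Core Period 2 dose | Responder goes to | Non-responder goes to |
|---|---|---|
| 150 mg | 300 mg | 600 mg |
| 300 mg | 300 mg | 600 mg |
| 600 mg | 600 mg | 600 mg |

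As assigned, non-responders are 0% of the 300 mg arm, and 100% of non-responders are in the 600 mg arm.

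**2. Non-responder share of the 600 mg arm.** The documents give neither response rates nor the Period 2 dose mix, so both are assumed. Let r be a response rate common to all doses, and m150 and m300 the fractions on the lower doses.

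Share s = (1 − r) / [1 − r(m150 + m300)]

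For example, with equal thirds and r = 0.3, s = 0.70 / (1 − 0.3 × 2/3) = 0.70/0.80 = 87.5%. With 15/15/70 and r = 0.7, s = 0.30 / (1 − 0.7 × 0.30) = 0.30/0.79 = 38.0%.

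| Assumed mix 150/300/600 | r = 0.3 | r = 0.5 | r = 0.7 |
|---|---|---|---|
| Equal thirds | 87.5% | 75.0% | 56.3% |
| 25/25/50% | 82.4% | 66.7% | 46.2% |
| 15/15/70% | 76.9% | 58.8% | 38.0% |

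With 206 enrolled (SAP 1.1), the expected 300 mg arm is 206 × r × (m150 + m300). This runs from about 19 (15/15/70, r = 0.3) to about 96 (equal thirds, r = 0.7).

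**3. Difference from case mix alone.** Suppose dose has no effect and risk differs by g points between non-responders and responders. The crude 600-minus-300 difference is (s − 0) × g.

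- g = 5: 1.9 to 4.4 points
- g = 10: 3.8 to 8.8 points
- g = 20: 7.6 to 17.5 points

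If responders carry the higher risk, the sign reverses. The documents do not give g.

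**4. What a breakdown can identify.** Splitting 600-600 by responder status gives two groups of responders kept on their dose, 600-600 and 300-300, which can be compared. Among core 150 mg and 300 mg participants, extension dose is fully determined by response, and all non-responders are on 600 mg. No table or adjustment separates dose from response there.

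**A qualification on the Safety Set.** The composition above is as assigned. The SAP's actual-treatment rule takes the most frequent dose including loading, with ties going to the earliest. An Arm 2 participant who stops after one dose (600) or two (600, 300) is therefore counted under 600 mg. This moves a few early-stopping responders into the 600 mg column and leaves the 300 mg column without non-responders, unless there are dosing errors.

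**The case against.** The strongest reply is that the plan makes no dose comparison. The objective is safety at two dose levels, estimands are marked not applicable, and both documents restrict the analysis to descriptive statistics. Non-random assignment is disclosed and the algorithm is printed in full. All of this stands, and it limits the harm to interpretation. It does not remove the harm: these tables are the whole primary analysis, and nothing carries the disclosure into the analysis sections.

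Prior dose may also matter less than it seems. Entry follows a 12-week core follow-up, and everyone is loaded again. Escalation occurs in both arms, because 150 mg responders move to 300 mg. These points weaken those two confounders but leave response selection untouched.

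A reader might infer more than the documents support:

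- *That 600 mg will look worse.* Nothing in the documents links the IRT label to adverse event risk. Change is normally counted from Week 4, so someone who improved before then can be labelled a non-responder.
- *That the 600 mg arm is a non-responder arm.* It also contains all core 600 mg responders.
- *That no safety table anywhere shows sequence.* Protocol 12.6 is blacked out, SAP numbering passes from 2.5 to 2.7, and treatment sequence is undefined. Only the visible text can be judged.
- *That stratified tables would recover the dose effect.* Step 4 shows they cannot.

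**Conclusion.** The point holds as a limit on interpretation. The assignment rule alone, with no assumption, establishes that the 300 mg arm is assigned only responders and the 600 mg arm every non-responder. The visible plan presents primary safety in those two pooled columns without a breakdown or caveat. No test or error rate is affected.

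The sizes, 38-88% non-responders at 600 mg and about 4-9 points of spurious difference per 10-point risk gap, are illustrations. They rest on assumed response rates, dose mixes and risk gaps and are not bounds; direction is unknown. The change is worth making because it costs little and improves what can be concluded. Even the 600-600 versus 300-300 comparison among responders would be non-randomised and conditional on response, and would pool cohorts with different responder definitions.

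**What to change.** In SAP 2.4, add overall summaries of TEAEs, SAEs, adverse events of special interest and adverse events leading to discontinuation, by core Period 2 dose to extension dose: 600-600 (split by IRT responder status), 300-600, 150-600, 300-300 and 150-300. Define treatment sequence in SAP 2.1 in the same terms, so that listings and tables agree. State beside the pooled tables that the 600 mg and 300 mg columns do not estimate a dose effect, and that dose and response cannot be separated among core 150 mg and 300 mg participants.

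The cost is a few more tables. The IRT already uses Period 2 dose and responder status, so no new data are needed. Some cells will be small: under the 15/15/70 mix with 30% response, 150-300 and 300-300 would each hold about 206 × 0.15 × 0.3 = 9 participants. Counts should therefore be shown with the percentages.
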